1.0 Objectives

1.1 Study Objectives

The purpose of this study is to extend previous research (R03 CA144435) and conduct a preliminary analysis of the effect of a brief dermatologist-delivered intervention (ABC intervention) on patients' skin cancer related outcomes. The long-term goal with respect to the ABC intervention is to conduct a large-scale randomized controlled trial (RCT) with multiple clinics. Specific research aims of the study include:

The first aim examines the efficacy of the Addressing Behavior Change (ABC) intervention versus treatment as usual (TAU) during a regular dermatological visit on patient reported number of UV protective behaviors (such as use of sunscreen) and UV risk behaviors (such as number of sunburns) using a longitudinal design (3 and 6 month).

The second aim of the study will evaluate moderating factors, such as gender and history of skin cancer, and mediating factors, such as attitudes and self-efficacy, which impact the efficacy

of the intervention. The mediating and moderating variables may help to identify those individuals whom the intervention is more (or less) effective.

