- 3) For those who are called and invited to participate over the phone by a PSHMC research assistant, the research assistant will explain the study, and if the patient is interested, the research assistant will obtain verbal consent to screen patients to see if they qualify for the study based on the inclusion/exclusion criteria. If they are eligible, they will then be formally invited. Potential participants interested in the study will be asked to arrive 25 minutes early for their appointment so that the consent form may be reviewed with them in its entirety and signed informed consent can be obtained in a private area of the clinic prior to the completion of the brief baseline survey. A log will be kept of all de-identified patients contacted via phone who declined participate when approached in the clinic (example: adult male #1 refused study due to time commitment).
- 4) In the first cohort in Spring 2016, we enrolled 27 participants who qualified after completing the screening. For the second cohort in Spring 2017, we plan to enroll an additional sample of 200 (100 per site). Based on the response rate of the first cohort in Spring 2016, we will invite up to 770 participants in Spring 2017. Once the target enrollment of 200 total (about 100 per site) is obtained, we will discontinue recruiting. The study will be split into 2 cohorts

– one taking place in Spring 2016 (n=27) and the other taking place in Spring 2017 (target n=200).

- 5) Participants who are interested and who qualify to participate will either: 1) be asked on the phone for their email address in order to send a copy of the consent form and reminder to arrive at their scheduled appointment 25 minutes prior to their scheduled time, or 2) receive a copy of the informed consent and a letter by mail reminding them to arrive at their scheduled appointment 25 minutes before their scheduled time to perform the written informed consent process and to complete the baseline survey. Participants will also be called 1-3 days before their scheduled appointment to remind them to arrive 25 minutes early (see reminder phone script).

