- 6) 1-month and 3-month follow-up surveys will be conducted online to reduce burden and allow participants to complete them from home. Participants can request mailed, paper-based surveys if they do not want to complete the online version of the survey. Paper-based cover letter and surveys will be mailed to participants' homes along with prepaid return envelopes. Both the online version of the follow-up surveys as well as the hardcopy surveys (which will include identical questions/prompts as the REDCap survey), will include the text at the beginning of the survey that states "By completing the following survey you are agreeing to take part in this research study. If you have any questions about the survey or your participation, please contact project coordinator, [name], at [contact] or [contact]". Participants will receive an invitation email, up to 5 reminder emails, and up to 3 reminder phone call attempts to complete each survey. During the baseline survey, participants will also be asked if they would like to receive SMS text message reminders to participate in the follow-up surveys. If participants opt into receiving SMS text message reminders, they will receive 2 text message reminders for each survey along with all other contact methods.

Subjects will be informed in the consent process:

"You should be aware that it is illegal in the Commonwealth of Pennsylvania to text while driving. It is also dangerous to pay attention to your cellular phone while driving, walking, or doing any activity that requires your attention. You should continue to exercise good judgment on this while participating in this study."

Please note: Mailed hardcopy surveys/letters will only be offered to individuals who indicate that they do not have access to the internet, not as an option for all participants. With the timeframe between the 1-month survey and the 3-month survey being shorter, we do not want there to be any overlap of surveys if participants are slow to mail back their responses.

Recruitment of Physician Interventionists:

- The dermatologists from the intervention site will undergo 1 session of training to deliver the ABC intervention, following the same protocol developed and used in the R03 study. A weekly scheduled journal club meeting will be cancelled and this training will take the place of it in the evening (instead of morning) and will require no additional time commitment from the dermatologists to participate in the training or study.

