4.3 Recruitment materials

See details of procedure in section 4.2

- 1) Options Pre-Note Initial Recruitment Letter
- 2) Options Phone Script Baseline Invite
- 3) Options Reminder Email for Baseline Participation
- 4) Options Phone Script for Baseline Survey
- 5) Options Reminder Letter for Baseline Participation
- 6) Options Phone Reminder Script for Baseline Survey
- 7) Options 1 Month Followup Survey Email Mail Invite
- 8) Options 1 Month Followup Survey Reminder Email
- 9) Options 3 Month Followup Survey Email Mail Invite
- 10) Options 3 Month Followup Survey Reminder Email
- 11) Options Followup Reminder Call Script
- 12) Options Followup Survey Text Message Reminder
- 13) Options Thank You Letter for Study
- 14) Options Collateral Contact Call Script
- 15) Options Collateral Contact Email Mailed Letter

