25.3 Aim 1: Evaluate efficacy of the ABC intervention

[name] (Co-I) will conduct all outcome analyses in order to avoid any bias. First a 2 (Group: ABC vs. Controls) x 3 (Time: baseline, 3 & 6 mo. follow-up) Mixed ANOVA will be conducted to test the intervention on a given outcome variable (e.g., use of sun protection). First, we expect to observe a main effect of Group with the highest reports of sun protection (and lowest reports of UV risk behaviors) occurring in our ABC condition. Second, we anticipate observing a Group x Time interaction with no differences between the groups at baseline but differences (lower risk in the ABC group) at each of the follow-ups. He will also assess the scientific and clinical significance of the effects utilizing the magnitude estimation approach described by Jaccard. Specifically, statistical significance refers to the case when the null hypothesis is rejected, whereas magnitude estimation approaches emphasize the size of the effect. To utilize magnitude

estimation approaches, the researcher must specify an a priori effect size that differentiates a trivial effect from a meaningful effect. If the effect size observed is less than the criterion for meaningfulness, then the result is deemed nonsignificant, even if the null is rejected. We will use Cohen's d statistic to assess clinical significance of the main effects and interactions. We will define an effect as clinically and statistically significant to the extent that the d is greater than or equal to .20.

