25.4 Aim 2: Evaluate moderators and mediators

We will also undertake a set of analyses that identify individual differences in intervention efficacy to examine for whom the intervention is more or less effective. Where the moderator variable is qualitative (e.g., gender), it will be included as another factor into the Mixed ANOVA described earlier. For example, a 2 x 3 x 2 (group x time x patient gender) on sun protection may be used to evaluate gender of the patient as a moderator. First, we will explore whether our effect of Group, where the lowest reports of UV risk behaviors occurring in our ABC condition, differs by the gender of the patient (a group x gender interaction). Second, we will explore whether our Group x Time interaction differs by gender (e.g., a significant group x time x gender interaction). These analyses will be repeated for each of the qualitative moderator variables and evaluated for clinical significance. For quantitative (ordinal or interval) moderator variables (e.g., age), we will calculate product terms between the moderator and group and then analyze the data using moderated regression following the logic in Jaccard & [name]. For mediation, we will use the joint significance test, which Monte Carlo simulations have shown has the most power and lowest Type I error rates relative to other approaches. We will evaluate model fit using global fit indices (e.g., CFI, RMSEA), and more focused indices that suggest specific areas of poor fit (modification indices). We will use bootstrapping where necessary to account for non-normal variable distributions. Using Amos 20.0, if both the a and b paths are significant at the .05 level there is evidence for mediation. The mediated effect is the product of a and b and provides an estimate of the strength of the mediated effect. When there is evidence of mediation, 95% confidence intervals using the bootstrap procedures in Amos can be calculated to provide a range of estimates for the mediated effect. If the confidence intervals do not contain zero there is evidence of statistically significant mediation. Figure 1.

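### The main 2 x 3 mixed ANOVA uses baseline, 3 and 6 months, but the trial surveys patients at baseline, 1 and 3 months

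*Combined protocol and SAP*

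**What the plan says.** Aim 1 (section 1.1) describes its comparison as "using a longitudinal design (3 and 6 month". SAP section 25.3 builds those times into the main efficacy analysis, a two-group "x 3 (Time: baseline, 3 & 6 mo. follow-up) Mixed ANOVA will be conducted to test the intervention on a given outcome variable". It predicts no group difference at baseline and then "differences (lower risk in the ABC group) at each of the follow-ups".

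Section 25.4 reuses the model for qualitative moderators. Of such a moderator it says "it will be included as another factor into the Mixed ANOVA described earlier", and it gives the example "a 2 x 3 x 2 (group x time x patient gender) on sun protection may be used". It names no time points of its own, so it takes them from 25.3.

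The operational sections give a different schedule. Section 4.2 says "1-month and 3-month follow-up surveys will be conducted online to reduce burden". The recruitment materials in 4.3 include "Options 1 Month Followup Survey Email Mail Invite" and a 3-month counterpart, but nothing for month 6. Sections 7.2, 7.3, 10.1, 10.2 and 19.0 all give 1 and 3 months. Section 7.3 limits patient participation to 4 months, and 19.0 puts the end of the study after the 3-month survey.

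Section 9.2 names the mixed ANOVA without time points.

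**The concern.** The analysis that decides Aim 1 cannot be run at the times the SAP gives. An analyst who reaches the data must either replace month 6 with month 1 or drop the empty level, and the SAP does not say which. These are different tests. The group main effect averages over whichever waves are included, and the d of at least 0.20 rule in 25.3 applies to main effects as well as interactions, so the choice could change the declared result.

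The claim is also affected. Sections 1.1 and 25.3 imply that behaviour change is assessed to 6 months, whereas the trial can support only 3. The two schedules also cover different seasons, which matters for sun protection and sunburn.

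**Working it through.** No stated power or sample-size figure is at issue. The check compares two lists of times.

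| Month | In 1.1 and 25.3 | Collected (4.2, 4.3, 7.2, 7.3, 10.1, 10.2, 19.0) |
|---|---|---|
| 0 | yes | yes |
| 1 | no | yes |
| 3 | yes | yes |
| 6 | yes | no |

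**Overlap.** Stated {0, 3, 6} and collected {0, 1, 3} share {0, 3}. Two of the three stated levels have data. The only other six-month period in the protocol (section 2.2) concerns dermatologists in the earlier R03 study, not a patient survey.

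**Follow-up length.** 6 / 3 = 2, so the stated follow-up is twice what is collected. 6 - 4 = 2, so month 6 falls 2 months past the participation limit in 7.3.

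**Surveys affected.** Take the intended enrolment of 227 (9.1 and 16.0) and assume complete data, because no retention figure is given.
- Planned surveys: 3 x 227 = 681.
- Matching a stated level (baseline, month 3): 2 x 227 = 454.
- Matching none (month 1): 227, and 227 / 681 = 33.3%.
- Planned observations at month 6: 0.

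The one-third share does not depend on the enrolment figure.

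**The tests an analyst could run.** Degrees of freedom at N = 227, complete data:
- Month 1 in place of month 6, Group x Time: (2-1)(3-1) = 2 and (227-2)(3-1) = 450, so F(2, 450).
- The same waves, Group x Time x gender: 2 and (227-4)(3-1) = 446, so F(2, 446).
- Empty level dropped, Group x Time: (2-1)(2-1) = 1 and (227-2)(2-1) = 225, so F(1, 225).

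Only the first choice keeps the three levels written in 25.3 and 25.4 and the plural follow-ups in 25.3. The 2 x 3 and 2 x 3 x 2 layouts then need no change.

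**Missing-data rules.** Section 25.2 offers EM or FIML for missing values. That addresses gaps in waves that are collected; it cannot supply a wave that nobody is asked to complete.

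**Season.** With baseline in April-May (7.3), month 1 falls in about May-June, month 3 in July-August and month 6 in October-November.

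**Cohort 1.** Section 4.2 reports that "In the first cohort in Spring 2016, we enrolled 27 participants who qualified after completing the screening", which is 27 / 227 = 11.9% of the intended enrolment. April-May 2016 plus 4 months ends by about 30 September 2016, some 6 months before Cohort 2 baseline starts in April 2017. Cohort 1 outcome data could therefore exist before any correction is made.

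**The case against.** The strongest reply is that these are two wrong labels. Both schedules have three waves, the model and its degrees of freedom survive correction, data collection does not change, and a sensible analyst would choose baseline, 1 and 3 months. The primary endpoint in 1.2 names no time, and a reader of 7.2, 7.3 or 19.0 would see that the last survey is at 3 months. All of this is true, and it makes the repair easy. It does not make the text usable: the labels define the time factor of the main test and the length of follow-up claimed, and nothing in the SAP tells the analyst which substitution to make.

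Three narrower points have some force.
- Month 1 is left out of the ANOVA in 25.3, but the regression and mediation models in 25.4 name no waves, so it is not ruled out there.
- The documents do not separately give the schedule that Cohort 1 followed. A remark in 4.2 that the gap between the two follow-up surveys is now shorter may hint at an earlier plan. Zero observations at month 6 therefore assumes that the current schedule applied to both cohorts.
- Section 7.3 gives the baseline period as approximately 8-10 weeks, so Cohort 1 could have finished some days after 30 September 2016. That is still well before April 2017.

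Nothing in the documents suggests that Cohort 1 outcomes were examined.

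**Conclusion.** The concern holds and should be corrected before the outcome analysis. Sections 1.1 and 25.3 conflict with every section that gives survey times, and no text resolves the conflict. As written, one of the three time levels in the main efficacy ANOVA is empty, a wave making up one third of planned surveys is left out of it, and the follow-up claimed is 6 months against 3 collected. The moderator ANOVA in 25.4 inherits the error.

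The survey counts and degrees of freedom assume N = 227, complete data and the 1- and 3-month schedule for both cohorts. The contradiction itself needs none of these assumptions.

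**What to change.** In 1.1 and 25.3, state the time factor as baseline, 1 month and 3 months. In 25.3, define the follow-ups at which a group difference is expected as 1 and 3 months. Limit the Aim 1 conclusion to 3 months. Section 25.4 names no times and then follows without its own edit.

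Date the change, make it before the outcome analysis, and state whether any Cohort 1 outcome data (n = 27) had been examined by then.

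The cost is wording in two sections and one dated statement; no survey, payment or visit changes. The real loss is that the trial then makes no claim about 6 months. Keeping that claim would mean adding a 6-month survey and extending participation past the 4-month limit, which costs far more. For Cohort 1, month 6 fell in about October-November 2016, before Cohort 2 began.

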6.3 Waiver or alteration of authorization statements of agreement Not Applicable

7.0 Study Design and Procedures

7.1 Study Design

This study will use a longitudinal design to compare the effect of the ABC intervention on the intervention group versus the control group receiving TAU. Participants will not be randomized to a group. Instead, patients who meet eligibility criteria at PSHMC will be invited to participate at the intervention site, and current patients who meet eligibility criteria at the clinic in State College will be invited to participate at the control site.

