9.0 Statistical Plan

9.1 Sample size determination

874 is the maximum number of patient participants to be enrolled. The number of participants that will be contacted (874) is much larger than the number we intend to enroll (227). Based on the response rate of the first cohort in Spring 2016, we are confident that the recruitment process explained above will yield the required number of participants within the proposed period.

27 participants were enrolled during the first cohort in 2016.

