9.2 Statistical methods

We will utilize a number of statistical methods. For example, basic t-tests and regression will be used for preliminary analyses. The majority of the analyses will center on two types: 1) moderated multiple linear regression (SEM models) for Aim 2 and 2) Mixed ANOVA for Aims 1 and 2.

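### Section 25.3 applies one success label to both the Group main effect and Group x Time without saying which decides, and a stable clinic difference passes in full into the Group effect

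*Combined protocol and SAP*

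**What the plan says.** Section 7.1 states that "Participants will not be randomized to a group". Sections 7.1 and 7.2 make Hershey the ABC site and State College the treatment-as-usual site, so arm and clinic are the same variable. Under 7.2 the baseline survey is completed before the patient sees the dermatologist.

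Section 9.2 assigns "Mixed ANOVA for Aims 1 and 2". Section 25.3 specifies it for Aim 1 as 2 groups by 3 times, with baseline as one of the times and no covariate named. Two results are expected:

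- "First, we expect to observe a main effect of Group with the highest reports of sun protection";
- "we anticipate observing a Group x Time interaction with no differences between the groups at baseline", with differences favouring ABC at each follow-up.

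Section 25.3 then uses Cohen's d "statistic to assess clinical significance of the main effects and interactions" and sets the rule "We will define an effect as clinically and statistically significant to the extent that the d is greater than or equal to .20". It adds the converse: "If the effect size observed is less than the criterion for meaningfulness, then the result is deemed nonsignificant, even if the null is rejected". It does not say which standard deviation defines d.

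Sections 1.2, 9.2 and 25.1 to 25.3 do not say which term decides efficacy. Nor do they say what follows if only Group is significant, or if the clinics differ at baseline.

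**The concern.** The Group main effect is the average difference between arms over all three waves, and one of those waves precedes any exposure to ABC. With one non-randomised clinic per arm, a difference in sun-protection habits that existed before the visit and persists through follow-up appears in that average undiminished. Equality at baseline is something 25.3 anticipates; the design does not secure it.

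Two errors are possible. A clinic difference favouring Hershey could meet the plan's criteria and be read as an answer to the question in 1.2, whether ABC was efficacious. A difference in the other direction could hide a real benefit. Either would misinform the large randomised trial that 1.1 gives as the long-term goal.

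**Working it through.** **Plan's own figure.** The plan gives no figure for the Group effect under a clinic difference. Section 25.1 states power above 0.90 for Aim 1, but names no contrast, correlation or alpha, so it can be neither confirmed nor refuted. The point does not depend on it.

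**Inputs from the documents.** N = 227 intended (9.1 and 16.0; 25.1 says 300). Groups are taken as equal, following the 100/100 target for Cohort 2 (16.0). The planning effect is d = .2 (25.1) and the label threshold is d ≥ .20 (25.3).

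**Assumptions not in the documents.** SD 1 at each wave; equal within-person correlation r = .3/.5/.7; two-sided alpha .05; no attrition or clustering; a clinic gap b that is constant over time; a follow-up effect δ, equal at both follow-ups. Triplets below are in the order of r.

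**Step 1: what each term estimates.** The ABC minus TAU differences at the three waves are (b, b+δ, b+δ).

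- Group main effect: b + (2/3)δ. The gap enters in full and the effect at two thirds. For δ = 0.2 and b = 0 it is 0.133 SD. A gap of −0.133 SD brings it to zero.
- Change from baseline to the mean of the two follow-ups: (b+δ) − b = δ. A constant gap cancels.

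**Step 2: false positives for Group (δ = 0).** The variance of a person's three-wave mean is V = (1+2r)/3 = .533/.667/.800. The standard error of the arm difference is √(4V/227) = .097/.108/.119. The noncentrality is b divided by that, on 225 df; for b = 0.2 it is 2.06/1.85/1.68.

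| Stable gap b | Group significant, r = .3/.5/.7 | Change contrast |
|---|---|---|
| 0.05 SD | 8/8/7% | 5% |
| 0.1 SD | 18/15/13% | 5% |
| 0.2 SD | 54/45/39% | 5% |

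At N = 300, b = 0.2 gives 66/56/49%.

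**Step 3: does the d rule filter these?** The smallest significant d is t(.975, 225) × √(4/227) = .26 if d uses the SD of person means. On the single-wave SD it is .26 × √V = .19/.21/.23. Nearly every significant Group effect therefore also earns the label. In the other direction, a true 0.2 SD follow-up effect with no gap has an expected Group d of .133/√V = .18/.16/.15 on the person-mean SD, and .133 on the single-wave SD. Both are below the threshold.

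**Step 4: power for δ = 0.2, b = 0, N = 227.**

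| Test | Basis | Power, r = .3/.5/.7 |
|---|---|---|
| Group alone | shift .133, V as above | .28/.23/.20 |
| Omnibus Group x Time (2 df) | λ = (227/4)(.0267)/(1−r) = 2.16/3.03/5.04 | .24/.32/.51 |
| Mean-change contrast (1 df) | variance 1.5(1−r) = 1.05/.75/.45 | .31/.41/.61 |
| Group or omnibus Group x Time | 1 − (1−.28)(1−.24), and so on | about .45/.48/.60 |
| Baseline-adjusted follow-up mean | variance (1+r)/2 − r² = .56/.50/.36 | .52/.56/.71 |

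The either-term row treats the two tests as independent, which holds under equal correlations. Its type I error is 1 − .95² = 9.75%, about 10%, even with no clinic gap. The baseline-adjusted contrast keeps about (1−r) of a stable gap: for b = 0.2, that is .14/.10/.06 SD.

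**The case against.** Much of the protection is already in the plan. Section 25.3 pre-specifies Group x Time and describes the right pattern for it, equality at baseline and separation afterwards, which a stable clinic gap would contradict. The Group sentence states an expectation, not a success rule, and the order of the two sentences need not be a ranking. A reader might infer that 25.3 lets a Group effect alone establish efficacy, or makes it the leading result. The text does not say so. What it leaves out is precedence, and it gives main effects the same d label as interactions.

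The size is also conditional. The documents give no clinic gap and no correlation, and both clinics recruit under the same eligibility rules and visit types (3.1, 4.1). At a gap of 0.05 SD the error rate is only 7 to 8%. The 54/45/39% needs a gap as large as the planned effect, so it should not be read as the error rate to expect.

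Finally, 1.1 calls the study preliminary, 7.1 is open about the lack of randomisation, and no change contrast removes differing time trends between clinics. All of this stands, and it limits the claim. It does not supply the missing rule: a Group effect with d ≥ .20 and no interaction would meet the plan's stated label, and 25.3 gives no ground for setting it aside.

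**Conclusion.** The point holds in limited form. Section 25.3 contains the right test but does not make it decisive, and it extends the success label to a term that carries any stable clinic difference in full and a true effect at two thirds. That structure follows from the design and needs no assumed value. The percentages rest on the assumed gap, correlation, equal groups and absence of attrition, and are illustrations.

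A reader might also infer that dropping the Group main effect costs no power. That is true only against Group alone, and only for r above .25, where 1+2r exceeds 2(1−r). Against a reading in which either term may support a claim, the mean-change contrast loses about 14 and 7 points at r = .3 and .5 and nothing at r = .7. The extra power of the either-term reading is bought with about 10% type I error.

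Provider clustering, covariate-by-time terms and the moderator analyses in 25.4 are not part of this point.

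**What to change.** In 25.3:

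1. State that the Group main effect alone is not evidence of efficacy and does not receive the d ≥ .20 label.
2. Name as the deciding contrast the ABC minus TAU difference in change from baseline to the mean of the two follow-ups. It is a 1-df component of the Group x Time interaction already planned. State which SD is used for d.
3. Report the result as a preliminary difference between the ABC clinic and the TAU clinic, in line with 1.1, because with one clinic per arm no analysis separates ABC from site-specific change.

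The follow-up times differ between 25.3 (3 and 6 months) and 7.2 (1 and 3 months). That needs reconciling separately; the contrast is defined the same way under either.

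The change is to SAP wording only, with no new data or visits. The cost is power: .31/.41/.61 for a 0.2 SD follow-up effect, against about .45/.48/.60 for the either-term reading and .52/.56/.71 for a baseline-adjusted contrast. Preferring change to baseline adjustment is a trade of precision for protection against a stable clinic gap. A team that judges such a gap unlikely could argue the other way, but should then say in advance how much of a gap would remain. The claim also becomes more modest.

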24.0 Appendix

25.0 Statistical Analysis Plan

25.1 Power/Sample Sizes

The sample sizes were chosen based on statistical, analytic, and theoretical considerations. For comparisons of the ABC vs. TAU controls on our outcome variables for Aim 1 (e.g., sun protection behaviors), our N should be able to detect effect sizes that correspond to small effects, Cohen's d = .2 or eta squares of 2%. The effect sizes are based on our pilot study examining patients' sunscreen use intentions following exposure to the ABC intervention (see preliminary studies section) and our studies examining group differences using motivational enhanced interventions to reduce tanning intentions and behaviors. Using power estimation procedures described in Cohen, the sample sizes should vield power of greater than 0.90 for the contrasts of interest. A second analysis that we will pursue will be moderated multiple linear regression or SEM models for Aim 2. [name] has special expertise in such analyses, where we test for effectiveness of the intervention as a function of a moderator variable at baseline (e.g., gender). With every moderator, our sample sizes for each group are reduced by approximately 50%. With our target N = 300 (at baseline), we will have sufficient samples to explore the potential of 2 moderators simultaneously and still have sample sizes that approximate n = 37 per group. Such Ns will also permit us to detect partial r2 sizes in the .04-.06 range and will have power of .70 or greater for the contrasts of interest.

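### SAP 25.3 requires an observed d of at least .20, the same effect 25.1 powers for, so success at a true d of .20 is capped near .50 for a signed contrast and the stated power above 0.90 cannot hold there

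*Combined protocol and SAP*

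**What the plan says.** SAP 25.1 says the Aim 1 sample should detect "small effects, Cohen's d = .2 or eta squares of 2" per cent, with "power of greater than 0.90 for the contrasts of interest". It describes this as detection of an effect and refers to no minimum observed effect.

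SAP 25.3 plans a 2 (group) x 3 (time) mixed ANOVA and adds a magnitude criterion. Cohen's d is to be used "to assess clinical significance of the main effects and interactions", and an effect counts as clinically and statistically significant when "the d is greater than or equal to .20". The criterion applies to the observed effect and takes precedence over the test: "If the effect size observed is less than the criterion for meaningfulness, then the result is deemed nonsignificant, even if the null is rejected".

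Two sample sizes appear. SAP 25.1 works from a target of 300 at baseline, while protocol 9.1 and 16.0 give an intended enrolment of 227.

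**The concern.** The effect used for power and the hurdle on the estimate are the same number. An estimate centred on .20 lands below .20 about half the time, and greater precision does not change that. The closing sentence of 25.3 can be read as requiring d of at least .20 alone, or d of at least .20 together with a significant test. Either way an observed d of .20 or more is necessary for success.

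The power figure in 25.1 therefore describes rejection of the null, which is not the decision 25.3 makes. Protocol 1.1 presents this study as a preliminary analysis on the way to a large multi-clinic randomized trial. A real effect of the size the plan itself calls meaningful could be reported as nonsignificant despite a rejected null, and that could count against the later trial.

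**Working it through.** **Inputs from the documents.** Powered effect d = .2 or eta squared 2%, and power above 0.90 (25.1); hurdle of observed d at least .20 (25.3); N = 300 (25.1) or 227 (9.1, 16.0); roughly equal groups (100 per site in cohort 2; protocol 4.2, 16.0); three occasions (25.3).

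**Assumptions.** Two-sided alpha .05, because 25.3 states no alpha for Aim 1. The between-wave correlation r is not given, so a range is shown. d is in single-wave SD units, and no dropout is allowed for. The .50 cap depends on none of these.

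**1. The two effects named in 25.1.** With two equal groups, eta squared = d²/(d² + 4). At d = .20 this is .04/4.04 = 0.99%. Eta squared 2% gives d = 2 x sqrt(.02/.98) = .286. These are different effects.

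**2. The stated power, ignoring the hurdle.** For one wave, SE(d) = sqrt(4/N), which is .133 at N = 227 and .115 at N = 300. Noncentral-t power:

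| True d | N = 227 | N = 300 |
|---|---|---|
| .20 | .32 | .41 |
| .286 | .57 | .69 |

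At d = .20, power of .90 needs 526 per arm. The claim of more than 0.90 is not reproduced by a two-group test. It can be reached with inputs the plan does not give. For example, the 2-df Group x Time test with f = d/2 = .10 and r = .5 has noncentrality .01 x N x 3/(1 - .5), that is 13.6 or 18.0, and power .92 (N = 227) or .97 (N = 300).

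**3. Adding the hurdle, signed contrast.** Success requires observed d >= max(.20, 1.96 SE). At true d = .20, P(observed d >= .20) is .501 at 150 per arm, .5003 at 526 and .500 at 50,000. Power to reject the null meanwhile rises to .90 at 526 per arm and .994 at 1,000.

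**4. Where the hurdle binds.** It binds only when 1.96 SE < .20.

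- *Single wave.* 1.96 SE is .26 (N = 227) or .23 (N = 300), so significance already demands more than the hurdle does. The hurdle binds only above N = 4 x (1.96/.20)² = 384.
- *Baseline versus mean follow-up.* SE = sqrt(1.5(1 - r) x 4/N). At r = .8 this is .0727 or .0632. Test power at d = .20 is P(Z < .20/SE - 1.96), that is .79 or .89. With the hurdle both become .50. It binds for r above about .61 (N = 227) or .48 (N = 300).
- *Three-wave group mean.* SE = sqrt((1 + 2r)/3 x 4/N). The hurdle binds for r below about .39 (N = 227) or .67 (N = 300).

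**5. Unsigned 2-df interaction.** With f = .10 and r from .3 to .7, the chance of meeting both the test and the hurdle is .54 to .57 at N = 227 and .54 to .56 at N = 300.

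**6. At eta squared 2% (d = .286).** The cap does not apply. In a two-group test the joint success is .57 (N = 227) or .69 (N = 300), and .90 needs about 447 per arm. For baseline versus mean follow-up at r = .8, it is P(Z < (.286 - .20)/SE), about .88 or .91.

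**7. True d at which the joint rule reaches .90:** max(.20, 1.96 SE) + 1.2816 SE.

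| Contrast | N = 227 | N = 300 |
|---|---|---|
| Single wave | .43 | .37 |
| Baseline versus mean follow-up, r = .8 | .29 | .28 |

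**The case against.** A minimum-observed-effect rule is a legitimate choice. About 50% success at the boundary is inherent in it, and when it is added to a test it is conservative and cannot inflate false positives. The study is preliminary and non-randomized. All of that stands. It does not rescue 25.1, which quotes power at exactly that boundary without the rule.

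Three stronger readings are tempting, and the documents do not support them.

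- *That the hurdle explains the low success of a single-wave comparison, or that more patients never help.* The .32 and .41 are ordinary power with the hurdle idle. For that contrast, raising N from 227 to about 384 lifts success from .32 to .50. Only beyond that does added N stop helping at d = .20.
- *That 0.90 is unattainable under the plan altogether.* 25.1 also names eta squared 2%, where the .50 cap does not apply. A plain two-group test still falls well short at the planned N, but a precise repeated-measures contrast can come close to .90 or pass it.
- *That .50 is an exact ceiling for every effect.* 25.3 also applies the hurdle to interactions, and an unsigned multi-df effect size gives somewhat more than .50. No case computed at d = .20 comes near 0.90.

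It might also be said that d = .20 is only a label for clinical relevance. The text does not allow that reading: a result below the criterion is called nonsignificant even when the null is rejected.

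**Conclusion.** The point holds for a true d of .20. For a signed contrast, success as 25.3 defines it cannot exceed about .50 at any N, and it is about .54 to .57 for the unsigned 2-df interaction at the planned sizes with r from .3 to .7. The stated power above 0.90 therefore cannot hold at that effect under the plan's own decision rule.

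The practical loss depends on the contrast. A single-wave comparison loses nothing to the hurdle at N = 227 or 300, where sample size is the limit. Baseline versus mean follow-up at r = .8 drops from .79 or .89 to .50. These contrast-specific figures rest on two-sided alpha .05, equal groups, no dropout and an assumed r. The discrepancy between 300 and 227 is a separate matter, and resolving it leaves the cap in place.

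**What to change.** In 25.3, judge statistical significance by the test, report d with its 95% CI, and use d = .20 as a descriptive benchmark that does not override the test.

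If the hurdle is kept as a decision rule, restate 25.1 as the probability of meeting the joint rule. That is at most about .50 at d = .20 for a signed contrast. State the assumed alpha, N and between-wave correlation, and give the true d at which .90 is reached for each named contrast.

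A confidence-limit version, calling a significant effect trivial only when its upper 95% limit is below .20, is not a useful substitute. A significant positive effect has an upper limit of at least 3.92 SE. That is .52 (N = 227) or .45 (N = 300) for one wave, and .29 or .25 for baseline versus mean follow-up at r = .8. Such a rule could never apply to a significant positive effect in these scenarios.

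The cost is SAP wording only, with no change to design or data collection. The downside is a less favourable stated power figure.
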